##### **Exploratory objectives:**

To explore biomarkers that could predict treatment response to avelumab such as: the tumor immunoscore, presence and extent of PD-L1 expression on tumor cells and microglia/macrophages within the tumor

To correlate the OS and PFS in relation to the baseline value and the change from baseline to week 52 visit and every 52 weeks /or end of study visit (depending on whether the latter occurs before or after week 260) neurocognitive function as measured by the evoked potential P300 (normal), the baseline corticosteroid dose, the total cumulative corticosteroid dose over the whole study duration, the total cumulative temozolomide dose per BSA since diagnosis and the presence and severity of immune related adverse events (irAE's).

To assess and compare above mentioned biomarkers in tissue samples from patients with second surgical resection ie treatment failures.

To assess in this GBM population the duration of pseudoprogression and the lagtime needed for immunotherapy to become effective.

**Study Design:** This is a single center, phase 2, open-ended, open label, add-on, single dose study in patients receiving standard therapy for newly diagnosed GBM with

a projected duration of 5 years (260 weeks). In total 30 patients who meet the entry criteria will be entered into the study within 3 weeks of finishing their last day of combined radiotherapy/temozolamide. Avelumab will be initiated concurrently with the initiation of the first 5 days, monthly cycle of temozolamide and continued until the occurrence of a termination event defined as one of the following: 1) clinical evidence of neurological deterioration resulting in an ECOG score of at least 3 or more, unexplained by other comorbidities, unchanged by an increase in corticosteroid dose and sustained for at least two weeks or 2) treatment emergent adverse event (TEAE) of grade 3 or more or 3) withdrawal of patient consent.

A local pathology report will constitute adequate documentation of histology for study inclusion.

The tumor block used for diagnosis of GBM must be collected for each patient and sent for MGMT assessment (if not already done), biomarker and immunoscore analysis. The availability of these samples is mandatory for the baseline visit.

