### **4.2. Treatment Phases of the Study**

**Combination Phase:** Upon completion of the standard combination therapy of radiotherapy (total dose 60 Gy, administered as daily 2Gy fractions, 5 days/week or as per local standard) and temozolomide (75 mg/m^2/day p.o. qd) and a treatment break of no more than 21 days, the combination phase will start. Patients will receive temozolomide and avelumab for 6 cycles of 28 days each. During the 1st cycle Temozolomide will be given the first 5 days at a dose of 150mg/m^2/day p.o. In the next cycle, the temozolomide dose should be escalated to 200/mg/m^2 if permitted by the patient's hematological and non-hematological toxicity profile (as per NCI-CTC AE version 5). The temozolomide dose will be adjusted according to hematological and non-hematological toxicity as per temozolomide's product monograph (appendix 4). Avelumab will be administered on day 1 and day 15 of each cycle at a dose of 10mg/kg IV. Avelumab therapy will be withheld according to the occurrence and severity of avelumab emergent adverse events as per table 3. Patients will continue the

combination of temozolomide (150 – 200mg/m^2 per day PO X5 days Q28days) and avelumab (at 10mg/kg dose, IV on days 1 and 15 per cycle) until 6 cycles are completed or until the occurrence of a termination event.

**Monotherapy Phase:** Upon completion of the Combination Phase or upon stopping temozolomide because of temozolomide related toxicity/tolerability issues or patient choice, the patient will continue into the avelumab Monotherapy Phase. Avelumab 10mg/kg IV Q2weeks will be continued as monotherapy until the occurrence of a termination event defined as one of the following: 1) clinical evidence of neurological deterioration resulting in an ECOG score of at least 3 or more, unexplained by other comorbidities, unchanged by an increase in corticosteroid dose and sustained for at least two weeks or 2) treatment emergent adverse event (TEAE) of grade 3 or more or 3) withdrawal of patient consent.

Patients who experience irAE's may according to table 3 directives have their avelumab therapy suspended.

The use of Bevacizumab or re-irradiation will not be allowed in the study and will be considered as evidence of a termination event.

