### **6.2. Criteria for Premature Withdrawal**

#### **Withdrawal from the study treatment /study**

The investigator can/must discontinue study treatment for a patient in the event of:

- Progressive disease (as per iRANO)
- Intercurrent illness
- Unacceptable toxicity (grade 3 or higher)
- Protocol violation
- Pregnancy
- Patient request
- In the case that the patient decides to prematurely discontinue study treatment he/she will be offered to continue into the Extended Safety Follow-up Phase
- In the case the patient decides not to or is unable to continue into the extended follow up phase then he/she will be withdrawn from the study. He /she will with the patient's permission be followed for survival assessment with monthly

telephone calls. Otherwise the patient will be considered lost to follow-up. The outcome of these discussions should be documented in both the medical records and in the CRF.

- Similarly, the investigator has the right to withdraw patients from the study in the event of intercurrent illness, unacceptable toxicity, protocol violation, pregnancy and administrative or other reasons. Patients have the right to withdraw from the study at any time for any reason.
- An excessive rate of withdrawals can render the study uninterpretable; therefore, unnecessary withdrawal of patients should be avoided.

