### **9.3.4. Assessments at end of study**

An end of treatment study visit will occur when:

- 1) Grade 3 or higher avelumab related toxicity occurs
- 2) Evidence as per the iRANO criteria of tumor progression occurs and patient does not wish to continue treatment
- 3) Patient wishes for any reason to discontinue treatment or withdraw from the study. Clinical evidence of neurological deterioration resulting in an ECOG score

of at least 3 or more, unexplained by other comorbidities, unchanged by an increase in corticosteroid dose and sustained for at least two weeks.

A history, physical and neurological exam will be performed by a physician. Laboratory test as per schedule will be drawn. If any of the latter have already been performed to confirm the AE or tumor progression on the basis clinical neurological deterioration, then they need not be repeated.

A study specified gadolinium enhanced MRI or CT scan will be performed within 2 weeks of the end of study visit for all patients after 52 weeks.

Patients however who discontinue the study treatment on the basis of avelumab treatment related AE's or clinical evidence of tumor progression a study specified MRI or CT scan will be done at the discretion of the investigator.

Patients who prematurely discontinue study treatment will be encouraged to continue into the Extended Safety Follow-up phase of the study

Patients who not only end treatment but also withdraw from the study, for any reason, will be encouraged to have telephone follow ups every month in order to obtain survival information with regards to OS. Pathology samples will be obtained for repeat biomarker analysis if a second tumor surgery occurs

**NOTE:** Since the actual duration of pseudoprogression and the time for immunotherapies to become effective in patients with GBM are still unknowns patients will be allowed at the investigator and patient discretion to continue on study treatment after confirmation of radiographic progression unless there is significant drug toxicity Grade 3 or higher AE's unrelated to avelumab such as those secondary to intercurrent illness or temozolomide therapy do not constitute for the purpose of this study a reason to withhold avelumab therapy or withdraw the patient from the study.

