## **10. INVESTIGATIONAL MEDICINAL PRODUCT**

### **10.1. Dose and Schedule of Test Drug**

Avelumab is a fully human IgG1 antibody directed against PD-L1. Avelumab binds PD-L1 and blocks the interaction between PD-L1 and its receptors PD-1 and B7.1. This removes the suppressive effects of PD-L1 on anti-tumor CD8+ T cells, resulting in the restoration of cytotoxic T cell response.

Avelumab will be administered intravenously every 14 days starting the same day as the first day of the first 5 days po temozolomide treatment. Temozolomide's 28 days cycle will be repeated 6 times or until grade 3 or higher temozolomide related treatment AE's. Avelumab will be continued IV q14 days for 260 weeks or until grade 3 or higher avelumab treatment-related AE's occurs and independent of whether the patient continues or completes the 6 cycles of temozolomide.

Avelumab may be withheld temporarily in the case of irAE according to the irAE's algorythms (table 3)

Temozolomide dose may be adjusted or withheld according to the directives in the temozolomide's product monograph (appendix 4)

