### **11.4. Treatment Emergent Adverse Event (TEAE) Requiring Avelumab Discontinuation or Modifications**

The following TEAE's require permanent treatment discontinuation of avelumab:

- **Any Grade 4 TEAE require treatment discontinuation with avelumab** except for single laboratory values out of normal range that are unlikely related to study treatment as assessed by the Investigator, do not have any clinical correlate, and resolve within 7 days with adequate medical management
- **Any Grade 3 TEAE's require treatment discontinuation with avelumab except for any of the following:**
  - Transient ( $\leq$  6 hours) Grade 3 flu-like symptoms or fever, which is controlled with medical management
  - Transient ( $\leq$  24 hours) Grade 3 fatigue, local reactions, headache, nausea, emesis that resolves to Grade  $\leq$  1

- Single laboratory values out of normal range (excluding Grade  $\geq 3$  AST or ALT combined with  $\geq 2$  ULN total bilirubin) that are unlikely related to study treatment according to the Investigator, do not have any clinical correlate, and resolve to Grade  $\leq 1$  within 7 days with adequate medical management
- Change in ECOG PS to  $\geq 3$  that does not resolve to  $\leq 2$  within 14 days (infusions should not be given on the following cycle, if the ECOG PS is  $\geq 3$  on the day of Avelumab administration)

- **Any Grade 2 TEAE should be managed as follows:**

If a Grade 2 ADR resolves to Grade  $\leq 1$  by the last day of the current cycle, treatment may continue.

- If a Grade 2 TEAE does not resolve to Grade  $\leq 1$  by the last day of the current cycle, infusions should not be given on the following cycle. If at the end of the following cycle the event has not resolved to Grade 1, the subject should permanently discontinue treatment with avelumab. TEAE (except for hormone insufficiencies, that can be managed by replacement therapy; for these hormone insufficiencies, up to 2 subsequent doses may be omitted).
- Upon the second occurrence of the same Grade 2 TEAE (except for hormone insufficiencies that can be managed by replacement therapy) in the same subject, treatment with avelumab has to be permanently discontinued.
- Infusion-related reactions, hypersensitivity reactions (Grades 1 to 4), and tumor lysis syndrome should be handled according to guidelines provided.

The Management for Symptoms of Infusion-Related Reactions are listed in the table below:

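### As it reads, the ECOG exception to the Grade 3 stop in Protocol section 11.4 is inverted: it spares a fall to ECOG 3 or worse that does not resolve within 14 days

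*Protocol*

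**What the plan says.** Protocol section 11.4 opens a list of events that require permanent discontinuation. Its Grade 3 rule is "Any Grade 3 TEAE's require treatment discontinuation with avelumab except for any of the following". Four items follow before the Grade 2 rule. The fourth is a change in ECOG performance status to 3 or worse that does not come back to 2 or better "within 14 days (infusions should not be given on the following cycle, if the ECOG PS is" 3 or more when avelumab is due).

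Elsewhere the Protocol treats a sustained fall in ECOG as a reason to end treatment. The Synopsis (Study Design) and section 4.2 name as the first termination event "clinical evidence of neurological deterioration resulting in an ECOG score of at least 3 or more, unexplained by other comorbidities", provided that more corticosteroid does not help and the decline lasts at least two weeks. Section 9.3.4 repeats this as a trigger for the end-of-treatment visit.

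The Grade 3 stop itself is worded in several ways:
- Synopsis and section 4.2: "treatment emergent adverse event (TEAE) of grade 3 or more", whether or not related to avelumab.
- Section 6.2, under a lead-in that says the investigator can or must stop: "Unacceptable toxicity (grade 3 or higher").
- Section 9.3.4, item 1: "Grade 3 or higher avelumab related toxicity occurs".
- Section 10.1: "Avelumab will be continued IV q14 days for 260 weeks or until grade 3 or higher avelumab treatment-related AE's occurs".

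The NOTE in section 9.3.4 says that Grade 3 or higher events unrelated to avelumab "do not constitute for the purpose of this study a reason to withhold avelumab therapy or withdraw the patient from the study".

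**The concern.** An exception to a stopping rule should describe the milder case. This one describes the worse case. An investigator who follows section 11.4 to the letter would hold avelumab with no stated limit in a patient who stays at ECOG 3, and would stop it for good in a patient who recovers within two weeks.

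Safety and tolerability is the primary objective, and the endpoint is built on avelumab discontinuations. A stop that points the wrong way invites different decisions for similar patients. It also blurs the split between permanent and transient discontinuation. Where a persistent fall is a Grade 3 event attributed to avelumab, section 11.4 says hold while sections 9.3.4 and 10.1 say stop.

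**Working it through.** The rule has no figure behind it, so the check is a comparison of the text.

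**Step 1. The four Grade 3 exceptions in section 11.4.**

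| Exception | Condition | Type |
|---|---|---|
| Flu-like symptoms or fever | 6 hours or less, controlled | transient |
| Fatigue, local reaction, headache, nausea, emesis | 24 hours or less, back to Grade 1 or below | transient |
| Single laboratory value | back to Grade 1 or below within 7 days | resolving |
| ECOG 3 or worse | not back to 2 or better within 14 days | non-resolving |

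Three of the four describe an event that goes away. Only the ECOG item describes one that does not.

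**Step 2. What the literal rule does**, if the fall is recorded as a Grade 3 event:
- Resolves within 14 days: not on the exception list, so permanent stop.
- Does not resolve within 14 days: on the exception list, so dose hold only.

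**Step 3. The Grade 2 rule in the same section.** A Grade 2 event still unresolved at the end of the following cycle leads to permanent discontinuation, with an allowance for hormone insufficiency. A persistent Grade 2 event therefore has a limit, while the ECOG item has only a hold.

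**Step 4. The ECOG stop elsewhere.** The Synopsis, section 4.2 and section 9.3.4 all end treatment for neurological decline to ECOG 3 or worse sustained for two weeks. Section 5.2 counts such a decline lasting more than two weeks as progression. The direction is the same each time: unresolved means stop.

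**Step 5. Relatedness.**
- Any Grade 3 treatment-emergent event ends treatment: Synopsis, section 4.2, and section 11.4 subject to its exceptions.
- Only avelumab-related Grade 3 events end treatment: section 9.3.4 item 1 and section 10.1.
- Unrelated Grade 3 events are no reason to withhold or withdraw: section 9.3.4 NOTE.
- Some first Grade 3 immune-related events allow avelumab to resume: Table 3, for example diarrhoea or colitis, rash, and the category for other immune-related events.

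These cannot all be followed for an unrelated Grade 3 event, and no text says which governs.

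**Step 6. When 14 days can be judged.** Infusion visits are 14 days apart with a window of 2 days either side (Table 1). The gap between consecutive visits therefore runs from 14 − 2 − 2 = 10 days to 14 + 2 + 2 = 18 days. If the fall is first recorded at one visit, a next visit at day 10 to 13 is too early to show that 14 days have passed without recovery.

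**The case against.** The strongest objection is layout. The list runs over a page break, and indentation cannot be relied on after it. The section opens as a list of events requiring permanent discontinuation. If the ECOG item belongs at that level, its wording is right and it matches the two-week ECOG stop elsewhere. It is also the only one of the four items that names no toxicity grade or graded event. This reading is possible. It is the less natural one, because the laboratory item just before it sits at the same level and can only be an exception. It calls for the same clarification in any case.

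The second objection is that little turns on the item, and most of this stands. Infusion is barred while ECOG is 3 or worse. Tumour-driven decline is caught by the first termination event. Section 6.2 allows a stop for intercurrent illness, and Table 3 stops avelumab for a Grade 2 or 3 immune-related event lasting 12 weeks or longer. No text equates ECOG 3 with a Grade 3 event.

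A reader might go further and infer that the ECOG item conflicts with the Grade 3 stop in all five other places where one appears. The documents do not support that as a point about ECOG. Sections 9.3.4 and 10.1 cover only avelumab-related events, and section 6.2 concerns unacceptable toxicity and leaves room for judgement. A Grade 3 stop without exceptions would clash equally with the other three exceptions and with Table 3.

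A reader might also try to put a probability on it. Section 2 reports treatment-related Grade 3 events in 99 of 1300 subjects (7.6%), and 30 × 99/1300 is about 2.3 patients. The next step needs the share who also fall to ECOG 3 or worse, which the documents do not give. The most frequent Grade 3 or higher events listed there include GGT, lipase and AST increases, which say little about performance status.

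**Conclusion.** The point holds: as it reads, the ECOG exception in section 11.4 is inverted and should be corrected. This rests on reading the item as an exception, which is the natural but not the only reading. If it was meant as a stand-alone stop, the inversion disappears but the text still needs to say so.

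The practical size is limited. The direct conflict is with the two-week ECOG stop for neurological decline in the Synopsis, section 4.2 and section 9.3.4. What remains is a contradictory instruction for a persistent avelumab-related fall, and no clear limit in section 11.4 for a persistent fall that is not neurological. For an unresolved fall attributed to avelumab, the combined primary-endpoint rate is the same under either rule, because permanent and transient discontinuations both count (Protocol 12.3.1, SAP 1.3.1); only the split between them can move. No expected number of patients should be quoted.

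The mismatch over relatedness is a separate, wider inconsistency that stands whichever way the ECOG item is read.

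**What to change.** 1. Reword the exception in section 11.4: *Change in ECOG PS to ≥3 that resolves to ≤2 within 14 days (no infusion while ECOG PS is ≥3).*
2. List separately, as a permanent stop: *ECOG PS ≥3 not resolved to ≤2 within 14 days, unless attributed to a cause unrelated to avelumab and to the tumour (section 9.3.4 NOTE).* Without that qualifier, the new item would stop avelumab for an unrelated illness, against the NOTE.
3. Judge it at the first infusion visit at least 14 days after onset, since the next visit can fall as early as day 10.
4. Align relatedness: limit the Grade 3 stop in the Synopsis, section 4.2 and section 11.4 to avelumab-related events, subject to the section 11.4 exceptions, with Table 3 governing immune-related events. Do not give section 11.4 blanket precedence. It currently covers any Grade 3 treatment-emergent event, so precedence would override the 9.3.4 NOTE and possibly Table 3.

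Cost: items 1 to 3 change one bullet, add one stop item and set its timing. Item 4 settles a choice that the Protocol now makes both ways, so it needs a decision by the sponsor-investigator. All of it goes through a protocol amendment under section 15.2. No new visits or data are needed, because Table 1 already marks ECOG at the infusion visits.

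### The Grade 2 hold-and-stop rule and the ECOG hold in Section 11.4 are timed in cycles, but avelumab is given every 14 days and the only defined cycle is 28 days, so two readings give different hold and stop dates

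*Protocol*

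**What the plan says.** Section 11.4 of the Protocol sets the Grade 2 rule in three steps. If the event is back to Grade 1 or less before the current cycle ends, treatment may continue. If it has not resolved "by the last day of the current cycle, infusions should not be given on the following cycle". If it is still unresolved when that following cycle ends, avelumab stops permanently. A second occurrence of the same Grade 2 event also stops avelumab, except for hormone insufficiencies managed by replacement. The hormone exception is counted in doses: "for these hormone insufficiencies, up to 2 subsequent doses may be omitted". The ECOG bullet in the same section uses the cycle unit again: "infusions should not be given on the following cycle, if the ECOG PS is" 3 or more on the day of administration.

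The cycle is defined elsewhere. Section 4.2 gives six 28-day cycles in the Combination Phase and states "Avelumab will be administered on day 1 and day 15 of each cycle at a dose of 10mg/kg IV". Section 10.1 attributes the cycle to the chemotherapy: "Temozolomide's 28 days cycle will be repeated 6 times". For avelumab alone, Section 4.2 gives only a two-weekly schedule, and Section 10.1 says "Avelumab will be continued IV q14 days for 260 weeks". No 14-day avelumab cycle is defined in either document.

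Some events have their own instructions. Infusion reactions, hypersensitivity reactions "and tumor lysis syndrome should be handled according to guidelines provided". Sections 4.2 and 11.6 refer to Table 3, which is headed as covering immune-mediated reactions.

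**The concern.** The unit of the rule does not match the schedule of the drug it controls. A 28-day cycle holds two infusions. If a first Grade 2 event starts between them, the second infusion falls inside the current cycle, so the rule as written does not require it to be withheld even if the event is ongoing. In monotherapy no cycle start or end is given, so the hold and stop dates depend on which unit the reader adopts.

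This is first a dosing-safety matter. It also reaches the analysis: in Protocol Section 12.3.1 and SAP Section 1.3.1 the primary endpoint rests on avelumab-related events that lead to transient or permanent discontinuation. For the events concerned, the unit can decide whether a patient has an endpoint event at all, or whether that event is transient or permanent.

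**Working it through.** **Inputs**

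- Cycle of 28 days, six cycles, infusions on days 1 and 15 (Section 4.2): 6 × 28 = 168 days = 24 weeks, and 6 × 2 = 12 infusions.
- Infusions therefore fall due on days 1, 15, 29, 43 and 57, whichever reading is used.
- Rule from Section 11.4: test on the last day of the current cycle, withhold during the next one, stop at the end of that one.
- r is the first day on which the event is Grade 1 or less.
- The event is a first occurrence, is not a hormone insufficiency, and lies outside Tables 2 and 3 and the tumor lysis guidance.
- Assumption: a withheld dose counts as a transient discontinuation.

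**Formula.** For cycle length L and an onset in the cycle that ends on day E, there is no hold if r ≤ E. Infusions due on days E+1 to E+L are withheld if r > E. Avelumab stops at day E+L if r > E+L. The same last-day test is applied to both readings.

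**Onset on day 2.** L = 28 gives E = 28 and E+L = 56. L = 14 gives E = 14 and E+L = 28.

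| r | 28-day reading | 14-day reading |
|---|---|---|
| up to 14 | no hold | no hold |
| 15–28 | no hold | day 15 withheld (transient) |
| 29–56 | days 29 and 43 withheld (transient) | permanent stop at day 28 |
| over 56 | permanent stop at day 56 | permanent stop at day 28 |

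The count of transient and permanent events taken together differs only at r = 15–28. At r = 29–56 only the type differs.

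**Onset on day 16.** L = 28 gives E = 28 and E+L = 56. L = 14 gives E = 28 and E+L = 42.

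| r | 28-day reading | 14-day reading |
|---|---|---|
| up to 28 | no hold | no hold |
| 29–42 | days 29 and 43 withheld (transient) | day 29 withheld (transient) |
| 43–56 | transient | permanent stop at day 42 |
| over 56 | permanent stop at day 56 | permanent stop at day 42 |

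The pooled count never differs here. Only transient versus permanent changes, at r = 43–56.

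**Onset to permanent stop**, over onset days 1 to 28: 56 − 28 = 28 to 56 − 1 = 55 days on the 28-day reading, and 28 − 14 = 14 to 28 − 1 = 27 days on the 14-day reading.

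**Monotherapy.** For a patient who completes six cycles and stays on treatment, 26 infusions fall due from week 0 through week 50, and 26 − 12 = 14 of them come after the last defined cycle (13 if Table 1's labelling of week 24 as Combination is followed). For these the rule needs a unit that the protocol does not supply.

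**Size in the endpoint.** Each patient added to or removed from the pooled count moves a rate among 30 patients by 1/30 = 3.3 percentage points. How many would move cannot be derived. Section 2 reports treatment-related fatigue in 16.3% and nausea in 8.3% at all grades, with no Grade 2 or duration breakdown.

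**The case against.** The strongest reply is that this is a slip of terminology. The hormone exception would add nothing if the ordinary hold already covered a two-infusion cycle, the ECOG bullet combines a 14-day limit with the day of avelumab administration, and in monotherapy the only stated interval is two weeks. This lean towards 14 days is real, but it does not settle the matter. The Grade 2 rule speaks of infusions in the plural on the following cycle, which fits a two-infusion cycle, and Section 4.2 defines exactly such a cycle.

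A second reply is that Section 4.2 sends more than immune events to Table 3: "Avelumab therapy will be withheld according to the occurrence and severity of avelumab emergent adverse events as per table 3". Table 3, however, is headed for immune-mediated reactions, and its residual row for suspected events needs Grade 2 or 3 signs suggestive of an immune cause. That row does hold avelumab pending investigation, which narrows the gap. Non-immune fatigue or nausea still falls under Section 11.4.

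A third reply is that practice would protect patients. Section 9.3.2 provides checks before every infusion with referral to a physician, this is a single center, and the investigator is free to hold. All of that stands, but Section 9.3.2 contains no Grade 2 hold criterion, and discretion does not supply a stop date.

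Three stronger inferences are not supported. A reader might infer that the rule orders the day-15 dose to be given; it only fails to require that it be withheld. A reader might infer that monotherapy has no workable Grade 2 rule; the second-occurrence stop and the dose-counted hormone exception still work there, and the rest is a choice between two readings. A reader might infer that most infusions in the trial are affected; a share near 90% would need treatment for the full 260 weeks, whereas Section 1.1.1 cites median survival of 15 months on standard therapy, and infusions are not events that reach the rule.

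**Conclusion.** The point holds in bounded form and should be fixed. Section 11.4 states a safety rule in a unit that does not match the avelumab schedule. The gap concerns first-occurrence Grade 2 events without guidance of their own; the ECOG hold has the same wording problem. For early-cycle onset the reading can decide whether a dose must be withheld, and so whether an endpoint event exists. For late-cycle onset it changes only the number of doses withheld, the stop date, and transient versus permanent.

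The practical size is unknown and probably small: the event must be related to avelumab, non-immune and still Grade 2 when a dose falls due. It would be wrong to infer that the primary result or the benefit criteria are compromised. The safety analysis is descriptive, and no decision threshold depends on this rule. The result rests on infusions given on schedule and on the same last-day test for both readings.

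**What to change.** In the Grade 2 and ECOG rules of Section 11.4, replace the cycle test with one infusion-day test that applies in both phases:

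- Withhold any avelumab infusion that falls due while the event is still Grade 2 or higher, or while ECOG PS is 3 or more.
- For Grade 2 events, stop permanently if the event is still Grade 2 or higher when the next infusion falls due, 14 days after the first withheld one. If the sponsor wants a longer limit, state it as an explicit number of days.
- Keep the hormone-insufficiency exception and the routing to Tables 2 and 3.

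An infusion-day test falls one day later than the last-day test used in the tables above. For onset on day 2, day 15 is withheld if the event is unresolved that day, and avelumab stops at day 29 if it is still unresolved then. A 28-day limit after the first withheld dose would put the stop at day 15 + 28 = 43. The literal reading stops at day 56.

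The cost is a short amendment to one section. Event onset and resolution dates (Section 11.13) and two-weekly pre-infusion checks and laboratory tests (Section 9.3.2) are already planned; the grade on the day a dose is due needs to be noted. The downside is somewhat more holds, and possibly earlier stops, for persistent non-immune Grade 2 events. The length of the stop limit is a clinical choice for the sponsor, and the hold correction does not depend on it.
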